4.2. Scientific Rationale for Study Design

This study will investigate the ADME of [¹⁴C]PF-07265803 and characterize plasma, fecal and urinary radioactivity and identify any metabolites of [¹⁴C]PF-07265803 in male participants. Only nonsmokers will be enrolled to minimize any potential effect on metabolism by smoking. Oral dosing will be administered in the absence of food, as food has been shown to potentially decrease exposures of PF-07265803 and mimics how PF-07265803 is being administered in the clinical program. Female subjects will be excluded to align with regulatory guidance. The ‘as low as (is) reasonably achievable’ (ALARA) principle prescribed by the FDA recommends that radiation exposure to subjects should be kept ALARA; therefore, if no specific reason exists to include females (ie, no available data suggest metabolism of the PF-07265803 is different in females versus males), then the radiation exposure to female subjects should ideally be kept at zero by not including females in this radioactivity study and only enrolling and dosing male subjects.

The potential risk of exposure to PF-07265803 in a sexual partner of a male participant in this study via ejaculate is possible, and therefore contraception (condom) use in male participants is warranted. The embryo-fetal developmental toxicity studies support the exclusion of pregnant women from clinical studies of PF-07265803 and the continued consideration that partners of study participants who are WOCBP use appropriate contraception in addition to condom use.

Banked Biospecimens will be collected and stored for further analyses which may, for example, provide greater understanding of the study intervention.

4.2.1. Choice of Contraception/Barrier Requirements

Nonclinical studies suggest risk for severe manifestations of developmental toxicity at relevant clinical exposures for PF-07265803. Therefore, the use of a highly effective method of contraception is required (see [Appendix 4](#)).

4.2.2. Collection of Retained Research Samples

Retained Research Samples will be collected and stored for further analyses which may, for example, provide greater understanding of the study intervention.

4.3. Justification for Dose

In more than 100 healthy participants and relatively healthy participants, 400 mg BID PF-07265803 has proven to be a well-tolerated dose. In Study ARRAY-797-223, 41 participants with OA of the knee received 400 mg BID for 28 days, and this dosing regimen was well tolerated. In PD studies using clinical samples, 400 mg QD doses of PF-07265803 provided inhibition of PD markers p38 pathway inhibition (cytokines, CRP) of greater than 80% (Study ARRAY-797-101). In a clinical study of pain relief (Study ARRAY 797-221), 400 mg QD of PF-07265803 provided maximal effect (associated with p38 MAPK inhibition), with 200 mg PF-07265803 providing significantly less benefit.

Doses utilized in the nonclinical studies of *LMNA*-related DCM, where positive effects on cardiovascular function and survival were demonstrated, provided exposure consistent with clinical exposure observed with 200 to 400 mg BID of PF-07265803. Study ARRAY-797-231 was a Phase 2, two-arm study designed to investigate the efficacy and safety of 48 weeks of treatment with PF-07265803 in 12 stable participants with DCM secondary to *LMNA* mutations. In this study, participants were alternately assigned to receive PF-07265803) at 100 mg BID or 400 mg BID resulting in n = 6 per dose group. Participants in the 100 mg BID dose group were allowed to dose escalate to 400 mg BID after 24 weeks of treatment. Three participants dose escalated to 400 mg BID after their Week 24 visits and all 3 remained at the 400 mg BID dose through Week 48. In this study PF-07265803 was generally well tolerated; most AEs were mild and only 1 participant discontinued due to a study intervention-related AE. There was also an apparent trend towards a dose response with greater efficacy observed with the 400 mg BID dose. Finally, the 400 mg BID dose of ARRY-371797 (PF-07265803) appeared to be associated with larger favorable changes in NT-proBNP concentration than the 100 mg BID dose in an analysis of aggregated mean change from baseline at all time points.

4.3.1. Dosimetry Calculations

Dosimetry calculations for this proposed [¹⁴C]PF-07265803 ADME study in healthy, male subjects are based on a tissue distribution study conducted with Sprague Dawley and Long Evans male rats receiving an oral dose of PF-07265803. Pharmacokinetic parameters and dosimetry projections were calculated for blood and tissues, including (but not limited to) International Commission on Radiological Protection (ICRP) 30 critical tissues of bones, bone marrow, lungs, testes (gonads), and thyroid and the four tissues with highest concentrations of radioactivity in tissues including the gastrointestinal tract, liver, renal cortex, and renal medulla.

The maximum whole-body exposure of humans to radioactivity from a 100 μ Ci PO dose of [¹⁴C]PF-07265803, which was predicted using this rodent tissue distribution data, was 0.00039 rem. This was approximately 0.013% of the 3 to 5 rem limit specified for whole-body exposure by the Code of Federal Regulations. The predicted exposure of the blood-

forming organs, gonads and 29 other tissues to radioactivity from an PO dose of 100 μ Ci of [^{14}C]PF-07265803 to humans were each less than 1.0% of the 3 to 5 rem limits specified by the Code of Federal Regulations.

The planned radioactive dose in the current study is 100 μ Ci of [^{14}C]PF-07265803; based on ICRP 30 weighting factors, this would result in an effective dose to the whole body of 0.39 mrem. The planned radioactive dose of approximately 100 μ Ci of [^{14}C]PF-07265803 is expected to provide a sufficient radioactive signal to achieve the study objectives with minimal radiation risk to subjects.

4.4. End of Study Definition

A participant is considered to have completed the study if he has completed all phases of the study, including the last scheduled procedure shown in [SoA](#) (ie, follow-up phone call).

The end of the study is defined as the date of the last scheduled procedure shown in [SoA](#) for the last participant in the trial.

5. STUDY POPULATION

This study can fulfill its objectives only if appropriate participants are enrolled. The following eligibility criteria are designed to select participants for whom participation in the study is considered appropriate. All relevant medical and nonmedical conditions should be taken into consideration when deciding whether a particular participant is suitable for this protocol.

Prospective approval of protocol deviations to recruitment and enrollment criteria, also known as protocol waivers or exemptions, is not permitted.

5.1. Inclusion Criteria

Participants are eligible to be included in the study only if all of the following criteria apply:

Age and Sex:

1. Participants must be male and ≥ 18 years of age at the time of signing the ICD.
 - Refer to [Appendix 4](#) for reproductive criteria for male ([Section 10.4.1](#)) participants.

Type of Participant and Disease Characteristics:

2. Male participants who are overtly healthy as determined by medical evaluation including medical history, physical examination, laboratory tests, and ECG monitoring.
3. Participants who are willing and able to comply with all scheduled visits, treatment plan, laboratory tests , lifestyle considerations , and other study procedures.

Weight:

4. BMI of 18.0 to 32 kg/m²; and a total body weight >50 kg (110 lb).

Informed Consent:

5. Capable of giving signed informed consent as described in [Appendix 1](#), which includes compliance with the requirements and restrictions listed in the ICD and in this protocol.

5.2. Exclusion Criteria

Participants are excluded from the study if any of the following criteria apply:

Medical Conditions:

1. Evidence or history of clinically significant hematological, renal, endocrine, pulmonary, gastrointestinal, cardiovascular, hepatic, psychiatric, neurological, or allergic disease (including drug allergies, but excluding untreated, asymptomatic, seasonal allergies at the time of dosing).
2. Any condition possibly affecting drug absorption (eg, gastrectomy, cholecystectomy, gastric bypass, duodenotomy, colectomy, history of inflammatory bowel disease).
3. History of HIV infection, hepatitis B, or hepatitis C; positive testing for HIV, HBsAg, or HCVA. Hepatitis B vaccination is allowed.
4. Participants with a history of irregular bowel movements; e.g., less than 1 bowel movement per day, regular episodes of diarrhea or constipation, irritable bowel syndrome (IBS) or lactose intolerance.
5. Other medical or psychiatric condition including recent (within the past year) or active suicidal ideation/behavior or laboratory abnormality or other conditions or situations related to COVID-19 pandemic (eg. Contact with positive case)] that may increase the risk of study participation or, in the investigator's judgment, make the participant inappropriate for the study.

Prior/Concomitant Therapy:

6. Use of prescription or nonprescription drugs and dietary and herbal supplements within 7 days or 5 half-lives (whichever is longer) prior to the first dose of study intervention with the exception of moderate/potent CYP3A inducers which are prohibited within 14 days plus 5 half-lives prior to the first dose of study intervention.. (Refer to Section [6.8 Concomitant Therapy](#) for additional details).
7. Current use of any prohibited concomitant medication(s) or those unwilling/unable to use a permitted concomitant medication(s). Refer to Section [6.8 Concomitant Therapy](#).

Prior/Concurrent Clinical Study Experience:

8. Previous administration with an investigational drug within 30 days (or as determined by the local requirement) or 5 half-lives preceding the first dose of study intervention used in this study (whichever is longer).

Diagnostic Assessments:

9. A positive urine drug test.
10. Screening and baseline supine BP >140 mm Hg (systolic) or >90 mm Hg (diastolic), following at least 5 minutes of supine rest. If BP is >140 mm Hg (systolic) or >90 mm Hg (diastolic), the BP should be repeated 2 more times and the average of the 3 BP values should be used to determine the participant's eligibility.
11. Screening and baseline standard 12-lead ECG that demonstrates clinically relevant abnormalities that may affect participant safety or interpretation of study results (eg, baseline QTcF interval >450 msec, atrial fibrillation, complete LBBB, signs of an acute or indeterminate-age myocardial infarction, ST-T interval changes suggestive of myocardial ischemia, second- or third-degree AV block, or serious bradyarrhythmias or tachyarrhythmias). If the baseline uncorrected QT interval is >450 msec, this interval should be rate-corrected using the Fridericia method and the resulting QTcF should be used for decision making and reporting. If QTcF exceeds 450 msec, or QRS exceeds 120 msec, the ECG should be repeated 2 more times and the average of the 3 QTcF or QRS values should be used to determine the participant's eligibility. Computer-interpreted ECGs should be overread by a physician experienced in reading ECGs before excluding a participant.
12. Participants with **ANY** of the following abnormalities in clinical laboratory tests at screening, as assessed by the study-specific laboratory and confirmed by a single repeat test, if deemed necessary:
 - AST **or** ALT level $\geq 1.5 \times$ ULN;
 - Total bilirubin level $\geq 1.5 \times$ ULN; participants with a history of Gilbert's syndrome may have direct bilirubin measured and would be eligible for this study provided the direct bilirubin level is \leq ULN.

Other Exclusions:

13. History of alcohol abuse or binge drinking and/or any other illicit drug use or dependence within 6 months of Screening. Binge drinking is defined as a pattern of 5 (male) or more alcoholic drinks in about 2 hours. As a general rule, alcohol intake should not exceed 14 units per week (1 unit = 8 ounces (240 mL) beer, 1 ounce (30 mL) of 40% spirit or 3 ounces (90 mL) of wine).
14. Positive urine drug screen or cotinine at screening or check-in, and positive urine alcohol at check-in.

15. Blood donation (excluding plasma donations) of approximately 1 pint (500 mL) or more within 60 days prior to dosing.
16. History of sensitivity to heparin or heparin-induced thrombocytopenia.
17. Unwilling or unable to comply with the criteria in the Lifestyle Considerations section of this protocol.
18. Investigator site staff or Pfizer employees directly involved in the conduct of the study, site staff otherwise supervised by the investigator, and their respective family members.
19. Subjects with exposure to significant diagnostic or therapeutic radiation (eg, serial x-ray, computed tomography scan, barium meal) or current employment in a job requiring radiation exposure monitoring within 12 months prior to check-in.
20. Subjects who have participated in more than 3 radiolabeled drug studies in the last 12 months (previous study to be at least 4 months prior to check-in to the study site where exposures are known to the investigator, or 6 months prior to check-in to the study site for a radiolabeled drug study where exposures are not known to the investigator). The total 12-month exposure from this study and a maximum of 2 other previous radiolabeled studies within 4 to 12 months prior to this study will be within the Code of Federal Regulations (CFR) recommended levels considered safe, per United States (US) Title 21 CFR 361.1.

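### Exclusion criterion 20 admits men with 3 radiolabeled studies in the past year, but its cumulative-exposure assurance covers at most 2

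*Protocol*

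**What the plan says.** Criterion 20 in Protocol Section 5.2 has two parts.

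- **Entry rule.** It excludes "Subjects who have participated in more than 3 radiolabeled drug studies in the last 12 months". A parenthesis adds two washouts. When the investigator knows the exposure from the earlier study, the gap must be 4 months or longer. The second washout is longer: "6 months prior to check-in to the study site for a radiolabeled drug study where exposures are not known to the investigator".
- **Exposure assurance.** The next sentence reads "The total 12-month exposure from this study and a maximum of 2 other previous radiolabeled studies within 4 to 12 months" and states that this total will be within "recommended levels considered safe, per United States (US) Title 21 CFR 361.1".

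Section 4.3.1 gives the only dose figure in the documents: "based on ICRP 30 weighting factors, this would result in an effective dose to the whole body of 0.39 mrem". It describes this exposure as "approximately 0.013% of the 3 to 5 rem limit specified for whole-body exposure by the Code of Federal Regulations".

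The SAP does not address prior radiolabeled studies.

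**The concern.** The two parts count differently. The first draws the line above 3 past studies; the second vouches for exposure with at most 2. A man with exactly 3 passes the entry rule and falls outside the assurance given for it.

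That assurance is the protocol's statement on cumulative radiation for volunteers who have been dosed before. Criterion 20 also accepts earlier studies whose exposures the investigator does not know. For those men the site cannot add up doses, so the number of studies is the practical link between eligibility and the assurance.

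Section 5 forbids waivers of entry criteria, so the criterion has to work as written, and staff or monitors could decide the 3-study case differently. Section 4.2 appeals to keeping radiation as low as reasonably achievable, and excludes women on that ground. An entry rule looser than the protocol's own exposure accounting sits badly with that. The matter concerns participant safety wording only, not the analysis.

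**Working it through.** **1. Counts side by side.** Let k be the number of radiolabeled studies in the 12 months before this one. The entry rule excludes when k > 3. The assurance applies when k ≤ 2.

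| k | Excluded (k > 3) | Covered (k ≤ 2) |
|---|---|---|
| 0, 1, 2 | No | Yes |
| 3 | No | **No** |
| 4 or more | Yes | No |

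The mismatch is exactly k = 3: 4 studies in total including this one, against 3 covered.

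**2. Do the washouts rule out k = 3?** No. With the latest study 4 months before check-in, 3 studies fit at months 4, 8 and 12. With the latest at 6 months, 3 fit at months 6, 9 and 12.

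**3. Does another criterion rule it out?** No.

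- Criterion 5 is investigator judgment and sets no count.
- Criterion 8 is a general investigational-drug washout of 30 days or 5 half-lives.
- Criterion 19 concerns diagnostic, therapeutic and occupational radiation.

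**4. The protocol's dose figure.** With d = 0.00039 rem, d/3 = 0.013% and d/5 = 0.0078%. The stated 0.013% is reproduced against the 3 rem end of the range. Both ends are carried below because the documents do not say which applies to the 12-month total.

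**5. Size if earlier studies delivered the same dose (assumption; no other doses are given).**

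- This study plus 2: 3d = 0.00117 rem = 1.17 mrem, which is 0.039% of 3 rem or 0.0234% of 5 rem.
- This study plus 3: 4d = 0.00156 rem = 1.56 mrem, which is 0.052% of 3 rem or 0.0312% of 5 rem.

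**6. How large would earlier doses have to be for the third study to matter?** For a limit L and an average dose x per earlier study, the total d + kx stays within L when x ≤ (L − d)/k. Allowing 3 instead of 2 changes the answer only when x lies between (L − d)/3 and (L − d)/2.

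| L | (L − d)/3 | (L − d)/2 | As multiples of d |
|---|---|---|---|
| 3 rem | 0.9999 rem | 1.4998 rem | about 2,564 to 3,846 |
| 5 rem | 1.6665 rem | 2.4998 rem | about 4,273 to 6,410 |

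**The case against.** The strongest reply is that criterion 20 contains its own cap. The sentence naming at most 2 earlier studies stands inside an exclusion criterion, so a site could read it as part of the rule and take the 3 as a total that includes this study. On that reading the numbers agree, and it may well be what the sponsor meant.

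It fits the text poorly. The rule is in the past tense and is applied before dosing, and the next sentence counts this study separately from the earlier ones. If that sentence is instead taken as a cap, the criterion states two different limits. Either route leads to the same correction.

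Three further points have force:

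- **Few men are affected.** If earlier studies were spaced at this protocol's 4-month minimum, 3 fit only at months 4, 8 and 12. With a 6-month washout, they need spacing of 3 months or less. The study enrolls about 6 men at one center.
- **Unknown exposures are not special to the third study.** A man with 1 or 2 such studies has the same difficulty, and the correction still admits him.
- **The protocol does not say that 3 earlier studies would breach a limit.** It is silent on that case.

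These points hold the matter to a minor one. They do not make the two counts agree.

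**Conclusion.** The concern holds. As written, criterion 20 admits up to 3 earlier radiolabeled studies in 12 months, while its exposure assurance reaches only 2. The count mismatch follows from the text alone and needs no assumption about dose.

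Its practical size does rest on an assumption, since doses from other studies are not given. With same-size studies the extra exposure is 0.39 mrem. The third study would decide compliance only if earlier studies averaged roughly 1.0 to 1.5 rem each (3 rem limit) or 1.7 to 2.5 rem each (5 rem limit). The finding is therefore a gap between an eligibility threshold and its stated justification, with no exceedance demonstrated. It is minor, but it should be corrected.

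**What to change.** In criterion 20, exclude men with more than 2 previous radiolabeled studies in the last 12 months, and state in a parenthesis that this study is not counted. The admitted counts become 0, 1 and 2, which match the assurance exactly. The 4- and 6-month washouts and the exposure sentence can stay as they are.

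The sponsor should confirm the intended count when making the edit. If 3 earlier studies really were meant, the exposure statement would have to be extended to them and supported.

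The cost is one number and a few words, with at most a slightly smaller pool of volunteers for a 6-man, single-center study.

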5.3. Lifestyle Considerations

The following guidelines are provided:

5.3.1. Meals and Dietary Restrictions

- Participants must abstain from all food and drink (except water) at least 4 hours prior to any safety laboratory evaluations and 8 hours prior to the collection of the predose PK sample.
- Water is permitted until 1 hour prior to study intervention administration. Water may be consumed without restriction beginning 1 hour after dosing. Noncaffeinated drinks (except grapefruit or grapefruit-related citrus fruit juices—see below) may be consumed with meals and the evening snack.
- Lunch will be provided approximately 4 hours after dosing.
- Dinner will be provided approximately 9 to 10 hours after dosing.
- An evening snack may be permitted.

- Participants will refrain from consuming red wine, grapefruit, or grapefruit-related citrus fruits (eg, Seville oranges, pomelos) from 7 days prior to the first dose of study intervention until collection of the final PK blood sample.
- While participants are confined, their total daily nutritional composition should be approximately 55% carbohydrate, 30% fat, and 15% protein. The daily caloric intake per participant should not exceed approximately 3200 kcal.
- To help assure regularity in bowel movements, nutritional composition should contain at least 15 g of fiber per 1000 kcal or fiber capsules containing the equivalent amount of fiber may be administered daily (beginning at least 8 hr after dosing).

5.3.2. Caffeine, Alcohol, and Tobacco

- Participants will abstain from caffeine-containing products for 24 hours prior to the start of dosing until collection of the final PK sample.
- Participants will abstain from alcohol for 24 hours prior (or as specified above for red wine) to admission to the CRU and continue abstaining from alcohol until collection of the final PK sample. Participants may undergo urine alcohol test at the discretion of the investigator.
- Participants will abstain from the use of tobacco- or nicotine-containing products for 3 months prior to dosing and during confinement in the CRU.

5.3.3. Activity

- Participants will abstain from strenuous exercise (eg, heavy lifting, weight training, calisthenics, aerobics) for at least 48 hours prior to each blood collection for clinical laboratory tests. Walking at a normal pace will be permitted;
- In order to standardize the conditions on PK sampling days, participants will be required to refrain from lying down (except when required for BP, pulse rate, and ECG measurements), eating, and drinking beverages other than water during the first 4 hours after dosing;

5.3.4. Contraception

The investigator or his or her designee, in consultation with the participant, will confirm that the participant has selected an appropriate method of contraception for the individual participant and his or her partner(s) from the permitted list of contraception methods (see [Appendix 4 Section 10.4.4](#)) and will confirm that the participant has been instructed in its consistent and correct use. At time points indicated in the [SoA](#), the investigator or designee will inform the participant of the need to use highly effective contraception consistently and correctly and document the conversation and the participant's affirmation in the participant's chart (participants need to affirm their consistent and correct use of at least 1 of the selected methods of contraception) considering that their risk for pregnancy may have changed since

the last visit. In addition, the investigator or designee will instruct the participant to call immediately if the selected contraception method is discontinued or if pregnancy is known or suspected in the participant or partner.

